## 8 Visit schedule and assessments

[Table 8-1](#) lists all of the assessments and indicates with an “X”, the visits when they are performed. All data obtained from these assessments must be supported in the subject’s source documentation.

Subjects should be seen for all visits/assessments as outlined in the assessment schedule ([Table 8-1](#)) or as close to the designated day/time as possible. Missed or rescheduled visits should not lead to automatic discontinuation. Subjects who prematurely discontinue the study for any reason should be scheduled for a visit as soon as possible, at which time all of the assessments listed for the final visit will be performed. At this final visit, all dispensed investigational product should be reconciled, and the AE and concomitant medications recorded on the CRF.

If the subject cannot or is unwilling to attend any visit(s), the site staff should maintain regular telephone contact with the subject, or with a person pre-designated by the subject. This telephone contact should preferably be done according to the study visit schedule.

The table indicates which assessments produce data to be entered into the clinical database (D) or remain in source documents only (S) (“Category” column).

Allowed visit windows are specified as follows:

- Screening assessments must occur within 84 days (12 weeks)  $\pm$  7 days prior to the enrollment as per [Table 8-1](#).
- For all screening visits a general  $\pm$  7 day visit window is allowed
- A  $\pm$  7 day visit window is allowed at Week 1 Day 1 (calculated from day of consent)
- A  $\pm$  3 day visit window is permitted on assessments at Week 3 Day 1.
- For all other dosing visits a general  $\pm$  7 day visit window is permitted on assessments
- A  $\pm$  7 day visit window for the end of treatment phase (last infusion + 2 weeks) is allowed.
- A + 7 day visit window for the end of the safety follow-up phase (last infusion + 105 days) is allowed.

Every effort should be made to follow the schedule outlined in [Table 8-1](#).

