## 8.1 Screening

After signing the study informed consent form (ICF), the screening assessments will be done within the screening window prior to Week 1 Day 1 (see [Table 8-1](#) for list of assessments to be performed). During this screening period, the prospective subjects will need to come to clinic for 3 visits: at Day -84, at Day -56, and at Day-28. At the first screening visit after signing the ICF (at Day -84), subjects will be briefed about the study requirements, including the instruction on how to record the priapic event(s) information as described in [Section 8.2.4](#). At the first screening visit, the prospective subjects will also be asked about their prior medical history related to priapism. This information will be collected via a priapism medical history questionnaire. The investigator will obtain consent/assent of subjects and/or parents according to local procedures. The additional details of the procedure of informed consent has been provided in [Section 7](#).

For laboratory evaluations used to determine eligibility, a repeated evaluation within the screening window is permitted for screening results out of the defined range before screen failing the subject. If the results from the central laboratory are partial or unavailable before the first infusion, local sampling is allowed. In addition, local re-sampling for platelet count test is allowed at any time in case of clumping or other issues reported from the central laboratory. If the repeated laboratory result meets the criteria, that result may be used to determine eligibility. If the repeated laboratory result does not meet the criteria, the subject will be considered a screening failure. For details of assessments, see [Table 8-1](#). Assessments of subject reported outcomes should be collected prior to any clinical assessments, drug dosing or diagnostic testing.

Re-screening of subjects is allowed if the subject has not been treated and was screened failed. In case of re-screening, site should enter this patient as a new subject with a new ID. A new informed consent form must also be signed. AEs and medical history will be assessed relative to the new informed consent date.

The study includes an optional biomarker component which requires a separate signature if the subject agrees to participate. For details, see [Section 7](#).

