2.1.1 General definitions

Study treatment: Study treatment refers to Crizanlizumab (SEG101) 5.0 mg/kg provided by IV infusion.

Study treatment start and end date: Study treatment start date is defined as the first date when a non-zero dose of study drug is administered and recorded on the Drug Administration Record (DAR) CRF page. Similarly, study drug end date is defined as the last date when a non-zero dose of study drug is administered and recorded on the DAR CRF page of the core study.

Baseline: Baseline period is defined as 12 weeks screening period prior to the first infusion of crizanlizumab 5 mg/kg at Week 1 Day 1.

- For the analysis purpose, in the tables and figures, baseline is considered from Day -91 to one day prior to dosing. Similarly, for "by week 26 analysis" from the first dose date to one day prior to Week 27 Day 1 visit date and for "by week 52 analysis" from the first dose date to one day prior to Week 53 Day 1 visit date will be considered.
- For subjects missing "Week 27 Day 1" visit or "Week 53 Day 1" visit, the scheduled visit day will be considered for cut-off.
- For listings, all available data will be considered.

For safety evaluations, the last available assessment on or before the date of start of study treatment is taken as "baseline" assessment. In case time of assessment and time of treatment start is captured, the last available assessment before the treatment start date/time is used for baseline.

For safety parameters (e.g. ECGs), where study requires multiple replicates per time point, the average of these measurements will be calculated for baseline (if not already available in the database).

In cases where multiple measurements meet the baseline definition, with no further flag or label that can identify the chronological order, then the following rule should be applied: If values are from central and local laboratories, the value from central assessment should be considered as baseline. If multiple values are from the same laboratory (local or central) or collected for ECGs or vital signs, then the last entry should be considered as baseline.

If subjects have no value as defined above, the baseline result will be missing.

Post baseline: Any measurements taken after baseline will be considered as post-baseline measurements.

Change from baseline: Post baseline value – baseline value

Percent change from baseline: (Post baseline value – baseline value) *100/ Baseline value;
(relative change from baseline).

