Visit-windows will be used for the data that is summarized by visit; they are based on the study evaluation schedule and comprise a set of days around the nominal visit day. For any assessment, there are the protocol defined scheduled visits around which visit windows were created to cover the complete range of days within the study. The visit windows are shown in Table 2-1. These apply to measurements taken at every visit.

When visit windows are used, all visits will be re-aligned, i.e., they will be mapped into one of the visit windows (e.g., if the Week 4 visit of a subject is delayed and occurs on Day 46 instead of on Day 29, say, it will be re-aligned to visit window Week 8). In the case of major deviations from the visit schedule, or due to unscheduled visits, several assessments of a subject may fall in a particular visit window (either scheduled or unscheduled). Statistical approaches to handle multiple assessments in a given visit window are specified below.

Table 2-1 Assessment windows for scheduled visits

Analysis Visit	Week (k)	Scheduled Day/ Target day [d=(k-1)*7+1]	Visit Window (in study days)
Baseline	BSL		-91 days to Day -1*
Week 1 Day 1	1	1	Day 1-7
Week 3 Day 1	3	15	Day 8-29
Week 7 Day 1	7	43	Day 30-57
Week 11 Day 1	11	71	Day 58-85
Week 15 Day 1	15	99	Day 86-113
Week 19 Day 1	19	127	Day 114-141
Week 23 Day 1	23	155	Day 142-169
Week 27 Day 1	27	183	Day 170-197
Week 31 Day 1	31	211	Day 198-225
Week 35 Day 1	35	239	Day 226-253
Week 39 Day 1	39	267	Day 254-281
Week 43 Day 1	43	295	Day 282-309
Week 47 Day 1	47	323	Day 310-337
Week 51 Day 1	51	351	Day 338-358
EoT	53	365	Day 359-371**

*Baseline measurement prior to first infusion of study drug.

**Based on medical judgement and data, upper limit of EoT will be extended upto maximum value day 447.

Laboratory assessments will be taken from Screening Visit 3 as per the protocol and the window does not include pre-screening period. Thus, window for laboratory assessments will be Day - 28 to Day -1.

Multiple assessments within visit windows

In order to summarize laboratory assessments over time (including unscheduled visits), the assessments will be time slotted. The following general rule will be applied:

- If more than one assessment is done within the same time window, the assessment performed closest to the target date will be used.
- If 2 assessments within a time window are equidistant from the target date, then the earlier of the 2 assessments will be used.

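### SAP 2.1.1 gives laboratory data two conflicting baseline rules without saying which governs; taken literally, the Day -28 to Day -1 window can drop protocol-compliant pre-treatment samples

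*SAP*

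**What the plan says.** **General rule.** Under the baseline definition in SAP 2.1.1, for safety evaluations "the last available assessment on or before the date of start of study treatment is taken as" baseline. Where clock times are recorded, it is the last value before the treatment start time. There is no earliest day. The paragraph closes: "If subjects have no value as defined above, the baseline result will be missing".

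**Window rule.** In the visit-windows part of the same section, the Baseline row of Table 2-1 ends at Day -1 and Days 1 to 7 form the Week 1 Day 1 row. A note on laboratory data adds: "Thus, window for laboratory assessments will be Day - 28 to Day -1".

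**Protocol timing.** Protocol 8.1 places the three screening visits "at Day -84, at Day -56, and at Day-28". Protocol 8 gives every screening visit 7 days either way, and a further 7 days either way to the first dose, counted from consent. Table 8-1 schedules hematology, chemistry, coagulation and urinalysis first at Screening Visit 3 and again at Week 1.

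**Outputs.** SAP 2.7.3 plans change from baseline, worst post-baseline CTCAE grade, and shift tables from baseline to the worst on-treatment value. SAP 2.1.1 starts the on-treatment period on the calendar day of the first dose.

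**The concern.** The two rules can return different baselines from the same data, and nothing in the SAP says which one the programmer should use. The window sentence is the more specific text, and the SAP says that visit windows apply to laboratory data, so following it would be a reasonable choice.

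That choice has two possible effects. A subject whose only screening sample was drawn before Day -28 has no baseline and drops out of the change-from-baseline and shift tables. A Day 1 sample drawn before the infusion cannot be baseline. Because SAP 2.1.1 treats anything after baseline as post-baseline, a value obtained before any drug can then count towards the worst post-baseline grade. In a single-arm study of about 36 subjects, a few such cases would be visible.

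The reason given for the window does not support its lower limit. The SAP says that the window leaves out the pre-screening period, but in the protocol pre-screening is the 14 weeks before consent, and consent is at about Day -84. Days -42 to -29 lie within screening.

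**Working it through.** **Inputs**
- Laboratory window: Day -28 to Day -1 (SAP 2.1.1).
- General baseline window for tables and figures: "baseline is considered from Day -91 to one day prior to dosing" (SAP 2.1.1).
- Nominal Screening Visit 3: Day -28, which is consent + 56 days when consent is at Day -84 (Protocol 8.1).
- Allowances: 7 days either way on screening visits and 7 days either way on Week 1 Day 1 (Protocol 8).
- Assumption: screening visits, like the first dose, are counted from consent. The protocol says this explicitly only for the first dose.

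**1. Reproducing the SAP's figures.** The general limit is 84 + 7 = 91 days, so Day -91 includes the 7-day allowance. Day -28 to Day -1 is the Screening Visit 3 column of Table 8-1 with no allowance. The same treatment would give 28 + 7 = 35, or Day -35.

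**2. Visit 3 window alone.** Day -28 plus or minus 7 runs from Day -35 to Day -21, which is 15 days. Seven of them, Day -35 to Day -29, lie outside the laboratory window.

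**3. First-dose window alone.** With Visit 3 exactly on time and the first dose 1 to 7 days late, the sample falls on Day -29 to Day -35. All seven cases lie outside.

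**4. Both windows.** Let *a* be the shift of Visit 3 and *b* the shift of the first dose, each from -7 to +7.
- Gap = (84 + *b*) - (56 + *a*) = 28 + *b* - *a*.
- Smallest gap: 28 - 7 - 7 = 14 days. Largest gap: 28 + 7 + 7 = 42 days.
- Compliant samples therefore range from Day -42 to Day -14.
- The gap exceeds 28 whenever *b* > *a*: 15 × 14 / 2 = 105 of 15 × 15 = 225 combinations, or 46.7%. This counts calendar combinations and does not estimate a share of patients.

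**5. The Day 1 sample under each rule**

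| | General rule | Window rule |
|---|---|---|
| Drawn before infusion, time recorded | Is the baseline | Cannot be baseline |
| Drawn after infusion, time recorded | Not baseline | Not baseline |
| No time recorded | Taken as baseline, even if drawn after the infusion | Cannot be baseline |
| Counted as on-treatment by date | Yes | Yes |

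The last row does not depend on the baseline rule. Under the general rule, a Day 1 pre-infusion value can be both the baseline and one of the on-treatment values from which the worst is taken. For that subject the worst on-treatment grade can then never be better than the baseline grade, so the shift table cannot show improvement.

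**6. Choosing among several values.** Table 2-1 resolves several values in a window by closeness to the target day, but the Baseline row has no target day. The window rule therefore does not say which of two samples in Day -28 to Day -1 is the baseline.

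**The case against.** The best defence is that the SAP already contains the right rule. The general safety definition accepts both an early Visit 3 sample and a Day 1 pre-infusion sample. The footnote to the Baseline row of Table 2-1 describes baseline as preceding the first infusion, and SAP 2.1 lets unscheduled pre-dose assessments count towards baseline. Visit windows are introduced for data summarized by visit, and the worst post-baseline grade is not a by-visit table. The window copies the Visit 3 column of Table 8-1, so a site that books within that column loses nothing. Protocol 8.1 and 8.3.2 also permit repeat screening laboratory tests.

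Much of this stands, and it rules out three stronger readings that a reader might infer.

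- *Baselines will go missing.* This follows only if the window overrides the general rule and no repeat sample falls inside it. The SAP does not say that it overrides.
- *Nearly half of subjects are affected.* The 46.7% would be a patient rate only if both visits were spread evenly and independently over their windows. The documents give no such information.
- *A pre-drug value is known to be misclassified.* Protocol Table 6-2 mentions laboratory tests on infusion days, but nothing says that the Week 1 Day 1 sample precedes the infusion.

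The defence does not remove the contradiction. The SAP applies visit windows to laboratory data by name, the Day -28 sentence is specific to laboratory data, and change from baseline is itself summarized by visit. Nor does the general rule settle the date-based on-treatment period.

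**Conclusion.** SAP 2.1.1 contains an unresolved conflict over laboratory baseline, and one of its two rules does not fit the protocol's visit windows. If that rule is applied, compliant Visit 3 samples from Day -42 to Day -29 fall outside it, and no Day 1 sample can be baseline. The number of subjects affected cannot be derived from the documents and may be 0% if all Visit 3 samples were drawn within Day -28 to Day -1.

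The Day -42 limit assumes that both visits are counted from consent; Visit 3's own window alone reaches Day -35. The Day 1 point assumes that some Week 1 samples are drawn before the infusion.

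It would be tempting to conclude that deleting the window sentence cures everything. It does not: the on-treatment period begins on the date of first dose, so a Day 1 pre-infusion value can still enter the worst on-treatment shift tables under the general rule.

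The effect is confined to laboratory safety summaries. The primary and secondary efficacy endpoints do not use this baseline. The correction should be made because a stated rule can give a wrong table and the remedy is nearly free.

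**What to change.** In SAP 2.1.1:
1. Delete the sentence that sets the laboratory window at Day -28 to Day -1.
2. State that the general safety rule (last value before the first infusion, with no earliest day) governs laboratory baseline, and that the Table 2-1 windows serve by-visit display only.
3. State how a Day 1 sample without a recorded time is classified. The date-only form of the general rule would accept a post-infusion value as baseline.

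In SAP 2.7.3:

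4. Exclude Day 1 values taken before the infusion from the laboratory worst post-baseline grade and the shift tables.

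The cost is a paragraph of SAP wording and one derivation in the laboratory dataset. No new data are needed. If tables have already been programmed, the study report should say which baseline rule was used and how many subjects had no laboratory baseline under it.

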### **Laboratory test interference with automated platelet counts**

Interference with automated platelet counts (platelet clumping) has been observed in patients treated with crizanlizumab in clinical studies, in particular when tubes containing EDTA were used. This may lead to unevaluable or falsely decreased platelet counts. Current clinical and pre-clinical data suggest this is an ex vivo effect that is EDTA- and time-dependent, without indication of platelet clumping, true reduction in circulating platelets or pro-aggregant effect in vivo.

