- Local lab results document an AE where the severity is worse than the one reported by the central lab, or
- Eligibility had to be based on the local lab results due to pending/missing central lab results.

Laboratory assessments can be repeated during the screening period as deemed appropriate by the investigator.

At any time during the study up to safety follow-up, abnormal laboratory parameters which are clinically relevant and require an action to be taken with study treatment (e.g. require dose interruption of study treatment, lead to clinical symptoms or signs, or require therapeutic intervention), whether specifically requested in the protocol or not, will be recorded on the AE eCRF page. The severity of laboratory data will be graded using the Common Terminology Criteria for Adverse events (CTCAE) version 5.0 or later. Additional analyses are left to the discretion of the investigator.

Specifically, for platelet count, local sampling will also be performed throughout the trial. To mitigate the potential for unevaluable or false low platelet counts (LPTs), it is recommended to run blood samples as soon as possible. Based on in vitro data, platelet clumping was observed in some donor samples as early as 4 hours following the addition of crizanlizumab. When needed, manual platelet estimation via blood smear to assess adequacy of the platelet count may be considered. Additional details on the measures to be used will be provided in the laboratory manual.

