- If multiple assessments are on the same date then the worst case will be used (minimum or maximum depending of the parameter direction).

Data from all assessments (scheduled and unscheduled), including multiple assessments, will be listed.

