2.7.3 Laboratory data

On analyzing laboratory values, data from all sources (central and local laboratories) will be combined as per Section 8.3.2 of the protocol. The summaries will include all assessments available for the lab parameter collected no later than 105 days after the last study treatment administration date. Following lab parameters will be analyzed :

Table 2-1

Test category	Test name
Hematology	Hematocrit, Hemoglobin, MCH, MCHC, MCV, reticulocytes (%), Platelets, Red blood cells, White blood cells, RBC Morphology, Differential (Basophils, Eosinophils, Lymphocytes, Monocytes, Neutrophils, Bands, Other
Chemistry	Alkaline phosphatase, ALT, AST, Gamma-glutamyl transferase (GGT), Lactate dehydrogenase (LDH), Bicarbonate, Calcium, Magnesium, Phosphorus, Chloride, Sodium, Potassium, Creatinine, Creatine kinase, Direct Bilirubin, Indirect Bilirubin, Total Bilirubin, Total Cholesterol, LDL, HDL, Total Protein, Triglycerides, Blood Urea Nitrogen (BUN) or Urea, Uric Acid, Amylase, Lipase, Glucose (non-fasting), estimated glomerular filtration rate (eGFR).
Urinalysis	Macroscopic Panel (Dipstick), done locally: Color, Bilirubin, Blood, Glucose, Ketones, Leukocytes esterase, Nitrite, pH, Protein, Specific Gravity, Urobilinogen Microscopic Panel (performed if dipstick is positive): Red Blood Cells, White Blood Cells, Casts, Crystals, Bacteria, Epithelial cells Urine creatinine/protein ratio, Microalbumin
Coagulation	Prothrombin time (PT) , International normalized ratio [INR]), Activated partial thromboplastin time (APTT)
Hepatitis markers	HBV-DNA, HbsAg, HbsAb, HbcAb, HCV RNA-PCR, HCV Ab
Additional tests	HIV Ab

For results reported by the central laboratory, continuous hematology and chemistry results will be summarized descriptively in SI units at each scheduled time point. Visits summaries will include baseline and post baseline visits, including early termination and Follow-Up. Changes from baseline will also be summarized at each time point.

The following summaries will be produced for laboratory data by laboratory parameters:

Separate summaries of change from baseline for each lab test category.

- Worst post-baseline CTCAE grade (regardless of the baseline status). Each subject will be counted only once for the worst grade observed post-baseline.

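### The SAP has no rule for clumped platelet counts, so the laboratory tables can overstate thrombocytopenia

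*SAP*

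**What the plan says.** On the artefact, Protocol 4.5 reports interference with automated platelet counts, mainly with EDTA tubes, and regards it as an ex vivo effect rather than a true fall: "This may lead to unevaluable or falsely decreased platelet counts". Protocol 8.3.2 then adds parallel sampling: "Specifically, for platelet count, local sampling will also be performed throughout the trial". Table 8-1 marks hematology and local platelets at the same visits, and its footnote applies the local sample to all subjects. Section 8.1 also allows local re-sampling when the central laboratory reports clumping.

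On the analysis, SAP 2.7.3 says that "data from all sources (central and local laboratories) will be combined as per Section 8.3.2 of the protocol". The same section then says: "For results reported by the central laboratory, continuous hematology and chemistry results will be summarized descriptively in SI units at each scheduled time point". Graded output is "Worst post-baseline CTCAE grade (regardless of the baseline status"), together with shift tables from baseline to the worst on-treatment value. SAP 2.1 puts all unscheduled assessments into shift and abnormality tables. SAP 5.3 assigns grades by program from the observed values and sets clinical assessment aside.

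For summaries over time, SAP 2.1.1 says: "In order to summarize laboratory assessments over time (including unscheduled visits), the assessments will be time slotted". Within a window it takes the value closest to the target day, and for ties on one date: "If multiple assessments are on the same date then the worst case will be used (minimum or maximum depending of the parameter direction". For baseline only, when several values qualify and their order cannot be told: "If values are from central and local laboratories, the value from central assessment should be considered as baseline".

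**The concern.** The protocol identifies a measurement error that works in one direction only and collects a second sample that could correct it. The SAP gives that second sample no corrective role. Wherever the rules choose between a clumped number and a valid one, they choose the lower, and no rule flags, excludes or overrules a clumped count.

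Laboratory safety belongs to a stated secondary objective, and Protocol 4.3 confirms that there is no control group. An artefact that appears only after exposure to the drug would look like a drug effect on platelets. With about 36 subjects, each subject wrongly graded moves a reported percentage by 1/36 = 2.8 points.

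**Working it through.** The plan states no thrombocytopenia rate, clumping rate or platelet SD, so there is no figure to reproduce. The check traces the rules and then illustrates their effect.

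**1. Which rule picks the platelet value in each output**

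| Output | Governing rule | Effect of a low clumped number |
|---|---|---|
| By-visit values and change | Time slots, worst value on a shared date (SAP 2.1.1); source unclear (SAP 2.7.3) | Pooled: selected over the local value on the same date. Central only: the local value is not used |
| Worst post-baseline grade | Worst grade over the period, observed values only (SAP 2.7.3, 5.3) | Sets the grade |
| Shift table | Worst on-treatment value, unscheduled included (SAP 2.7.3, 2.1) | Sets the shift |
| Listings | All values | Shown beside the others |
| Adverse event tables | AE CRF page (SAP 2.7.1) | Not driven by these rules |

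**2. One subject (illustration).** Take a true count of 300 x 10^9/L and a clumped central reading at 20% of it: 0.20 x 300 = 60. The local reading is 300, and min(60, 300) = 60. By the grade limits in Protocol Table 6-2, 60 is Grade 2 (below 75, not below 50). Pooled or central only, the subject is Grade 2. With the valid local count, the artefact gives no grade.

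**3. Chance of at least one clumped sample.** Table 8-1 gives Weeks 3 to 51 every four weeks, (51 - 3)/4 + 1 = 13 visits, plus end of treatment and follow-up: 15. With a clumping probability q per sample (assumed, independent between visits), the chance is 1 - (1 - q)^15:

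- q = 1%: 14.0% (about 5 of 36 subjects)
- q = 2%: 26.1% (about 9)
- q = 5%: 53.7% (about 19)
- q = 10%: 79.4% (about 29)

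**4. Simulated share with a worst count below 75 x 10^9/L (Grade 2 or worse).** The assumptions, none from the documents except the visit count, are: median 330; log-SD 0.35 between and 0.12 within subjects; 5% assay noise; clumping in central samples only; every clumped sample reported as a number; 20,000 simulated subjects.

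| Clumped | Read at | Pooled minimum | Central only | Local preferred |
|---|---|---|---|---|
| 1% | 50% of true | 0.3% | 0.3% | 0.0% |
| 1% | 20% of true | 9.4% | 9.3% | 0.0% |
| 5% | 20% of true | 35.8% | 35.8% | 0.0% |
| 10% | 20% of true | 54.4% | 54.4% | 0.0% |
| 10% | 10% of true | 78.5% | 78.5% | 0.0% |

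Pooled minimum and central only barely differ. The excess arises because clumped counts are neither excluded nor overruled, and the same-day rule adds almost nothing to the graded tables.

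**5. What the same-day rule does by itself.** For two readings with independent errors of SD s, the expected minimum lies s/sqrt(pi) = 0.564 s below a single reading. For an assumed s of 10 to 30 x 10^9/L, that is 5.6 to 16.9. In the simulation, 0.564 x 0.05 x 352 = 9.9, which matches the fall in the mean from about 352 to 342 without any clumping. The share with a worst count below 150 rises only from 5.7% to 6.5%, and the share below 75 stays at 0.0%.

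**The case against.** The strongest reply is that taking the worst value is a conservative convention for descriptive safety tables, that every value is listed, and that adverse event tables rest on the investigator's report. The last two points are true and limit the consequences. They do not repair the summary tables: a listing corrects no percentage, and a value believed to be an artefact gives no useful conservatism.

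Several stronger readings are tempting, and the documents do not support them.

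- A reader might blame the same-day rule for the excess. That rule serves summaries over time. The worst-grade and shift tables would take the low value without it. SAP 2.7.3 and Protocol 12.6.1 may also confine by-visit hematology to central results, in which case no central-local minimum is taken there.
- A reader might infer that baseline always uses the central value, so that one reading is compared with the lower of two. The default is the last assessment before treatment. Central precedence is only a tie-break when the order of values is unknown.
- A reader might say that the clumped value always prevails. An unevaluable sample yields no number. Clumping reported by the central laboratory may already be marked, though the SAP says nothing about using such a mark. Re-sampling may fall on another date.
- A reader might assume that a local count is in the database for every visit. Protocol 8.3.2 lists conditions for entering local results, and none covers a normal local count that contradicts a low central one. Whether those conditions also govern the scheduled local platelet samples is not clear. If they do, the correcting value may be missing, which makes the gap worse.

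The laboratory manual, which is not available here, may contain further platelet measures. It could improve the data, but it does not change the derivation rules in the SAP.

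**Conclusion.** The gap is real. Following the SAP as written gives a wrong grade or shift whenever a clumped sample is reported as a number low enough to cross a limit, even if a valid local count exists. The direction is known: toward more thrombocytopenia. The size is not known, because it depends on how often clumping occurs, how low the counts read, and how often the result is a number rather than unevaluable.

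The tables can overstate thrombocytopenia; the documents do not show that they will. The percentages in step 3 are assumed chances of at least one clumped sample, not predicted rates of false thrombocytopenia. Protocol 8.3.2 reports clumping in only some donor samples, and clustering within subjects would lower the share affected. The 0.0% for local counts rests on the assumption that local samples do not clump, which the documents do not state.

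The point concerns laboratory summaries only. It does not touch the primary endpoint or the adverse event tables. It should be corrected, because the affected tables describe platelet safety without a comparator and the remedy is small.

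**What to change.** Add a platelet-specific derivation to SAP 2.1.1 and 2.7.3:

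1. Exclude platelet results flagged as clumped or unevaluable, from either source, from by-visit change, worst-grade and shift tables. Use the valid result from the same visit where there is one, and list the excluded values. The flag should rest on the laboratory's report and not on the count being low, so that true falls are kept.
2. Exempt platelets from the same-day worst-case rule, and state one source precedence that applies at baseline and after baseline.
3. Reconcile the two source statements in SAP 2.7.3 for platelets (all sources combined, or central results only).
4. Make sure that the scheduled local platelet counts are entered in the eCRF.
5. Provide a sensitivity table that includes the flagged values, so that the effect of the exclusion can be seen.

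The cost is SAP wording, one extra derivation, one extra table and, where local counts were not entered, some data entry at sites. The small downside is that one table may mix two laboratories' reference ranges.
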